2. LIST OF ABBREVIATIONS

Abbreviation	Definition
AE	Adverse event
AEM	Adverse event monitoring
AG	Analysis Group, Inc.
AIDS	Acquired immune deficiency syndrome
AJCC	American Joint Committee on Cancer
CHF	Congestive heart failure
COPD	Chronic obstructive pulmonary disease
CTCAE	Common Terminology Criteria for Adverse Events
CVD	Cerebrovascular disease
ECOG	Eastern Cooperative Oncology Group
eCRF	Electronic case report form
FDA	Food and Drug Administration
GPP	Guidelines for Good Pharmacoepidemiology Practices
IRB	Institutional Review Board
IEC	Independent Ethics Committee
IMDC	International Metastatic Renal Cell Carcinoma Database Consortium
IO	Immuno-oncology
IQR	Interquartile range
ISPE	International Society for Pharmacoepidemiology
ISPOR	International Society for Pharmacoeconomics and Outcomes Research
MSKCC	Memorial Sloan Kettering Cancer Center
NCI	National Cancer Institute
NIS	Non-interventional study
PD-1	Programmed death-1
PD-L1	Programmed death-ligand 1
RCC	Renal cell carcinoma
SD	Standard deviation
STROBE	Strengthening the Reporting of Observational Studies in Epidemiology
US	United States
VEGF	Vascular endothelial growth factor

4. AMENDMENTS AND UPDATES

NONE.

5. MILESTONES

Milestone	Planned Date
Start of data collection	30 November 2020
End of data collection	31 January 2021
Final study report	31 July 2021

6. RATIONALE AND BACKGROUND

An estimated 400,000 new cases of kidney cancer, of which renal cell carcinoma (RCC) accounts for approximately 90%, are diagnosed worldwide every year.¹⁻³ RCC comprises 2-3% of all adult malignancies with an estimated 63,000 incident cases and 14,000 deaths from RCC annually in the United States (US).⁴ The exact cause of RCC is not well understood, but inherited and acquired mutations in oncogenes, such as von Hippel-Lindau, fumarate hydratase, and folliculin genes, may cause kidney cells to become cancerous. Obesity, hypertension, smoking, occupational exposure to toxic compounds such as cadmium and asbestos, and male gender are potential risk factors for triggering the genetic mutations,^{1,2} but many gene changes are random idiopathic events. Due to the lack of early symptoms and clinical indications of disease, up to 30% of patients with RCC are diagnosed with advanced or metastatic disease.⁵ Prognosis is poor among advanced RCC patients, with 5-year survival rates of approximately 8%.⁶ The burden of advanced RCC is projected to grow with the aging population and increasing prevalence of risk factors for RCC, such as obesity and hypertension.^{2,3}

During the last decade, targeted therapies, which are agents that target the vascular endothelial growth factor (VEGF), the VEGF receptor, or the mammalian target of rapamycin, became standard of care for patients with advanced RCC.⁷ Since 2005, several targeted therapies have been approved for the treatment of advanced RCC in the US, including axitinib (Inlyta[®]), sunitinib (Sutent[®]), bevacizumab (Avastin[®]), sorafenib (Nexavar[®]), pazopanib (Votrient[®]), cabozantinib (Cabometyx[®], Cometriq[®]), everolimus (Afinitor[®]), and temsirolimus (Torisel[®]).^{7,8} Targeted therapies have been associated with improved progression-free survival and overall survival, favorable side effect profiles, and improved health-related quality of life.⁹⁻¹⁵

Yet, recent advancements in immuno-oncology (IO) therapeutic agents have changed the treatment paradigm for advanced RCC. IO therapies work by blocking immune checkpoints (eg, programmed death-1 [PD-1]/PD-ligand 1 [PD-L1]) and restoring tumor-specific T-cell-mediated immune responses,^{16,17} and have demonstrated antitumor activity and durable responses in patients with advanced RCC.^{18,19} Specifically, the KEYNOTE-426 trial demonstrated that treatment-naïve advanced RCC patients who were treated with axitinib in combination with pembrolizumab had significantly longer overall survival, progression-free survival, and objective response rate compared to sunitinib,²⁰ leading to US Food and Drug Administration (FDA) approval of axitinib in combination with pembrolizumab for first-line advanced RCC treatment in April 2019. In addition, the JAVELIN Renal 101 trial showed significantly longer progression-free survival among advanced RCC patients who received avelumab plus axitinib than with sunitinib in first-line,²¹ leading to FDA approval of axitinib in combination with avelumab for first-line advanced RCC treatment in May 2019.

While axitinib has generally demonstrated a favorable tolerability profile in real-world studies,^{22,23} there is currently limited information on the real-world adverse event (AE) profile of axitinib in combination with IO therapies. In addition, the effect of dose reductions and treatment interruptions used to manage and resolve AEs occurring among patients with advanced RCC who use axitinib in combination with IOs is not well understood. Given this gap in the literature, AG will conduct a physician panel-based chart review to describe how dose reductions or treatment interruptions related to axitinib (in combination with IO therapy including avelumab or pembrolizumab) can be implemented to potentially manage and resolve AEs occurring among patients with advanced RCC. In this way, the study could help demonstrate that AEs associated with axitinib may be mitigated without excess use of healthcare resource use or additional treatment burden to patients beyond modifications related to axitinib.

7. RESEARCH QUESTION AND OBJECTIVES

The specific objectives of the study are as follows:

1. Describe incident AEs experienced among patients with advanced RCC who received first-line axitinib in combination with IO therapies.
 - Type and seriousness of AEs (ie, diarrhea, fatigue, hypertension, nausea, palmar-plantar erythrodysesthesia [hand-foot syndrome]).

- Proportion of patients who experienced repeated AEs.
- Time from treatment initiation to AE onset, overall and by type and seriousness of AEs.

2. Among patients with advanced RCC who developed incident AEs while receiving first-line axitinib in combination with IO therapies, characterize and describe management strategies for AEs, stratified by type and seriousness of AEs.

- Proportion of patients who used each of the following management strategies:
 - No action for axitinib and IO therapy;
 - No action for axitinib, but treatment modification for IO therapy (ie, treatment interruption, treatment discontinuation);
 - Axitinib dose reduction, but no action for IO therapy;
 - Axitinib treatment interruption, but no action for IO therapy;
 - Axitinib treatment discontinuation, but no action for IO therapy;
 - Axitinib dose reduction, and treatment modification for IO therapy;
 - Axitinib treatment interruption, and treatment modification for IO therapy;
 - Axitinib treatment discontinuation, and treatment modification for IO therapy.
- Average axitinib dose reduction (absolute and percentage change), where applicable.
- Duration of treatment interruption, where applicable.

3. Assess the frequency of and time to AE resolution (from AE onset and initiation of management strategy, separately) among patients with advanced RCC who developed incident AEs while receiving first-line axitinib in combination with IO therapies according to different management strategies implemented, stratified further by type and seriousness of AEs, as allowed by sample size.

[figure not shown]
The above objectives will also be conducted for repeated AEs of the same type.

8. RESEARCH METHODS

8.1. Study Design

A retrospective physician panel-based chart review study in the US will be conducted. The index date will be defined as the initiation of first-line axitinib (used in combination with IO therapy) on or after May 2019, which marks FDA approval of axitinib in combination with avelumab for first-line advanced RCC treatment. The baseline period will be defined as the 12-month period prior to the index date. The observation period will be defined as the time from index date to the earliest of initiation of a second line therapy, death, loss to follow-up, or date of chart abstraction. During the observation period, onset, management, and resolution of AEs will be assessed. The study design scheme is depicted in Figure 1.

Figure 1. Study Design Scheme

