8.3.3. Characterization of AEs

The following variables, to the extent they are available, will be assessed during the observation period:

- Type of AE, as defined by Common Terminology Criteria for Adverse Events (CTCAE):
 - Diarrhea, characterized by an increase in frequency and/or loose or watery bowel movements;
 - Fatigue, characterized by a state of generalized weakness with a pronounced inability to summon sufficient energy to accomplish daily activities;
 - Nausea, characterized by a queasy sensation and/or the urge to vomit;
 - Hypertension (new and worsening), characterized by a pathological increase in blood pressure;
 - Palmar-plantar erythrodysesthesia (hand-foot syndrome), characterized by redness, marked discomfort, swelling, and tingling in the palms of the hands or the soles of the feet.
- Serious AE.
 - As specified by the FDA, an AE is considered serious when the patient outcome is: death, life-threatening, hospitalization (either initial admission or prolongation of hospitalization), disability or permanent damage, or congenital anomaly/birth defect.
 - Date(s) of AE onset.
 - Date(s) of AE resolution.

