8.3.4. Management Strategies for AEs

The following variables, to the extent they are available, will be assessed during the observation period:

- Type of management strategy:
 - No action for axitinib and IO therapy;

- No action for axitinib, but treatment modification for IO therapy (ie, treatment interruption, treatment discontinuation);
- Axitinib dose reduction, but no action for IO therapy;
- Axitinib treatment interruption, but no action for IO therapy;
- Axitinib treatment discontinuation, but no action for IO therapy;
- Axitinib dose reduction, and treatment modification for IO therapy;
- Axitinib treatment interruption, and treatment modification for IO therapy;
- Axitinib treatment discontinuation, and treatment modification for IO therapy.
- Treatment modification for axitinib:
 - Date(s) of dose reduction;
 - Modified dosage of axitinib;
 - Date(s) when treatment was halted and reinitiated;
 - Date(s) treatment was discontinued.
- Treatment modification for IO therapy:
 - Date(s) when treatment was halted and reinitiated;
 - Date(s) treatment was discontinued.

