8.7.4. Analysis of Resolution of AEs

The proportion of patients achieving resolution of AEs will be described, overall and by type and seriousness of the AEs. The time to resolution from AE onset and from initiation of management strategy will be calculated for all AEs experienced including repeated AEs. The time to resolution of AE (from the onset of AE and from the initiation of management strategies) will be separately estimated using Kaplan-Meier analysis; median time to event will be reported. Analyses will be conducted separately by type of management strategy.

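### AE resolution is not followed past second-line start, which may cut it off unequally across management strategies, plausibly more after discontinuation

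*Combined protocol and SAP*

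**What the plan says.** Section 8.1 closes the observation period at the "earliest of initiation of a second line therapy, death, loss to follow-up, or date of chart abstraction" and adds: "During the observation period, onset, management, and resolution of AEs will be assessed". Section 8.3.3 introduces the AE variables with "The following variables, to the extent they are available, will be assessed during the observation period"; the list includes "Date(s) of AE resolution". Neither section extends follow-up for an AE still open at the switch.

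Section 8.3.4 defines eight management strategies. Two involve stopping axitinib: "Axitinib treatment discontinuation, but no action for IO therapy" and "Axitinib treatment discontinuation, and treatment modification for IO therapy".

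Objective 3 (section 7) asks for the frequency of resolution and the time to it, by strategy. Section 8.7.4 answers with a proportion ("The proportion of patients achieving resolution of AEs will be described, overall and by type and seriousness of the AEs") and with times that "will be separately estimated using Kaplan-Meier analysis; median time to event will be reported", and has the analyses run separately for each strategy. It gives no censoring rule, no treatment of death, and no rule for how an AE open at second-line start counts in the proportion. The limitations in section 8.9 do not raise the point.

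**The concern.** The rule that ends follow-up is linked to the thing being compared. A patient cannot begin second line without leaving first-line axitinib/IO, and one way of leaving is itself a strategy under study. Patients kept on treatment with no action, a reduced dose or an interruption need a further step before they reach second line. If patients who discontinue switch sooner, they have less time in which a resolution can be recorded, and their proportion resolved falls even when their AEs clear just as fast.

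On the crude proportion, that would favour dose reduction and interruption, the two approaches that section 6 hopes to show can manage AEs. The study is descriptive, but these side-by-side figures are its main product.

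The loss could not be repaired afterwards. Under section 8.6 physicians keep no decoding key, and under section 8.9 entries cannot be audited or queried. A resolution date not taken at abstraction is gone.

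**Working it through.** The plan states no resolution rate, second-line rate or power figure, so there is nothing of its own to reproduce. What follows is an illustration on assumed inputs.

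**Inputs**
- End of observation, the window for resolution dates, and the summaries by strategy: sections 8.1, 8.3.3 and 8.7.4.
- Assumed: exponential time to resolution with the same median in every strategy (30 days; range 14 to 90).
- Assumed: exponential time to second-line start, with a share p switching within 90 days of AE onset (0 to 60%).
- Assumed: other observation ends T = 90 or 365 days after onset. The 3-month minimum in section 8.2.1 runs from treatment start, not from AE onset, so it does not guarantee 90 days.

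**Crude proportion resolved**

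λ = ln 2 / median, μ = −ln(1 − p) / 90, and

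proportion recorded as resolved = λ/(λ + μ) × [1 − exp(−(λ + μ)T)].

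For a median of 30 days and T = 90, λ = 0.02310:
- p = 0 (no cut-off at the switch): 1 − exp(−0.02310 × 90) = 87.5%.
- p = 10%: μ = 0.00117; 0.952 × 0.8875 = 84.5%.
- p = 40%: μ = 0.00568; 0.803 × 0.925 = 74.3%.
- p = 60%: μ = 0.01018; 0.694 × 0.950 = 65.9%.

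The gap between 10% and 40% switching is 84.5 − 74.3 = 10.2 points, with identical true resolution. For other medians:

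| Median (days) | Gap, T = 90 | Gap, T = 365 |
|---|---|---|
| 14 | 7.6 | 8.0 |
| 30 | 10.2 | 14.9 |
| 60 | 9.1 | 23.0 |
| 90 | 7.4 | 26.3 |

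**Kaplan-Meier median, with the switch treated as censoring**
- *Switching independent of resolution.* With a true median of 30 days, the estimate stays at 29.9 to 30.1 days for p = 10%, 40% and 60%. There is no bias.
- *Slow resolvers switch sooner.* Half the AEs resolve at half the base rate and half at twice the base rate, and the switching rate is doubled in the slow half and halved in the fast half. The true median is 27.9 days. The estimate is 27.7, 26.8 and 25.9 days at base p of 10%, 40% and 60%. Over 180 days the crude proportion falls from 93.7% to 87.5%, 71.9% and 63.1%. The median looks better while the proportion looks worse.
- *Stronger dependence, both directions.* Resolution medians are 15 and 90 days in equal halves, with a true overall median of 32.6 days. If slow resolvers switch at a median of 30 days and fast ones at 120, the estimate is 28.8 days. With those reversed it is 38.0 days.
- *Second line starts only after the AE clears.* Nothing is lost: the crude proportion is 93.7% and the median is unchanged.

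**The case against.** Several points on the other side are sound.

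- **No second-line data.** The documents give no rate, timing or reason for second-line start, overall or by strategy. A reader might infer that second line mainly follows discontinuation and that the other strategies are hardly touched. The documents do not support that. A patient managed by dose reduction can switch later, and one who stops axitinib but continues IO may not start second line at all.
- **No coding rule.** A reader might infer that an AE open at the switch is recorded as unresolved, or that deaths are simply censored. Section 8.7.4 says neither. What is documented is the absence of a rule.
- **Kaplan-Meier can absorb the cut-off.** Earlier exit alone does not move the median when switching is independent of resolution. Larger contrasts can be produced for the crude share: if every patient switches and nothing else ends observation, it is 91% for a second-line median of 300 days and 50% for 30 days. Those figures do not carry over to the Kaplan-Meier analysis.
- **The cut-off has a rationale.** Once a new drug starts, persistence or clearing of an AE can no longer be credited to the axitinib/IO strategy. This stands, and it is a reason not to make the post-switch version the sole or primary analysis.
- **The study is descriptive.** Section 8.5 says no hypothesis is tested. That lowers the stakes, but a follow-up rule linked to strategy still distorts a descriptive proportion.

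None of this answers the crude proportion, which Objective 3 requires and which section 8.7.4 does not adjust for unequal follow-up.

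**Conclusion.** The concern holds as a plausible but unquantified differential truncation. Resolution dates stop at second-line start, results are shown by strategies that include discontinuation, and the crude proportion is exposed to unequal follow-up. With 10% against 40% switching, the spurious gap is about 7 to 10 points in a 90-day window and 8 to 26 points in a 365-day window. These figures rest on assumed exponential times and assumed switching shares. The gap disappears if switching is equally frequent across strategies or always waits for resolution.

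The Kaplan-Meier median is affected only if switching depends on the state of the AE, and it can then move either way. It would therefore be wrong to conclude that discontinuation must look worse on the time analysis. The documents establish neither the size nor the direction of any bias in that median.

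**What to change.** 1. In sections 8.1 and 8.3.3, keep second-line start as the end of the window for new AE onset. For AEs with earlier onset, collect the resolution date through to resolution, death, loss to follow-up or abstraction.
2. In the eCRF, record the second-line start date and the reason observation ended.
3. In section 8.7.4, report resolution by strategy both cut at second-line start and followed past it. The choice of primary version can be left open.
4. Use time-based estimates, such as cumulative incidence of resolution at set days from onset, rather than the crude proportion alone. Treat death as a competing event, and state how AEs open at each type of exit enter the estimates.
5. Tabulate, by strategy, why each unresolved AE left observation. This shows directly whether the truncation is unequal.

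The cost is wording in three sections and one or two date fields, taken from a chart the oncologist already has open; section 8.2.1 requires access to complete records. Section 8.4.1 allows the eCRF and protocol to be updated after the pilot. The downside is that post-switch resolution may reflect second-line drugs, which is why both versions are shown. Some post-switch dates may also be missing, for instance if care has moved elsewhere.

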8.2. Setting

8.2.1. Inclusion Criteria

Physicians meeting the following criteria will be invited to participate in the chart review study:

- Specialty in oncology.
- Access to complete medical records for at least one patient with advanced RCC who meets the patient eligibility criteria.

Eligible oncologists will be asked to select up to three patients meeting the following criteria for inclusion in the chart review study:

- Confirmed diagnosis with advanced RCC.
- Treated with first-line axitinib/IO combination therapy at or after diagnosis.
- Experienced at least one AE (ie, diarrhea, fatigue, nausea, hypertension, and palmar-plantar erythrodysesthesia [hand-foot syndrome]) while treated with axitinib/IO combination therapy.

- Age 18 years or older at the time of advanced RCC diagnosis.
- Initiated axitinib/IO combination therapy at least 3 months prior to the start date of medical chart abstraction to ensure sufficient follow-up time.

In the event that an oncologist has more than three eligible patients, the electronic case report form (eCRF) will have an underlying program that requires the oncologist to select patient charts based on a randomized sequence of letters. Specifically, the program will produce a random letter and request the oncologist to pull the first eligible patient chart with the last name that corresponds to the random letter. If there are no eligible patients whose last name begins with the first letter in the sequence, then the next letter in the order of the sequence will be shown. The random process will repeat for each new patient chart to be completed by the oncologist, until chart abstraction is completed for three eligible patients or until the physician has identified all eligible patients.

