8.3.1. Physician Characteristics

The following variables will be collected once for each physician participating in the study:

- Geographic region (ie, Northeast, Midwest, South, West, Other).
- Practice setting (ie, academic-based, community-based).
- Practice size (ie, solo [1 physician], small [2-10 physicians], medium [11-50 physicians], large [≥ 51 physicians]).
- Years in practice since completion of oncology training (ie, <1 year, 1-5 years, 6-10 years, 11-20 years, >20 years).
- Total number of unique advanced RCC patients seen per year.
- Percentage of advanced RCC patients prescribed first-line axitinib in combination with IO therapies in the past year.

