8.4. Data Sources

AG will contract with a physician panel vendor, Medefield America Limited LLC, to conduct an oncologist panel-based medical chart review in the US. Medefield has access to a large panel of physicians in a wide range of geographic locations. Oncologists will be recruited based on their medical specialty and selected for the study based on the eligible criteria. Each oncologist will complete eCRFs for up to three patients, with each chart review taking approximately 30 minutes to complete. The study will be double-blinded (physicians will be blinded to study sponsor and study sponsor will be blinded on physicians recruited to participate).

Oncologists will abstract data from medical charts of eligible patients using an online eCRF, which AG and the physician panel vendor will jointly develop specifically for this study. Medefield will set up a web-based portal with consistency checks, quality control, and validation processes built into the eCRF to ensure data quality. To capture all relevant information necessary for the study objectives, the eCRF may include both structured

(eg, multiple choice, select all options that apply) and unstructured fields (eg, open-ended responses).

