8.5. Study Size

Approximately 200 oncologists may be recruited by the physician panel vendor to abstract medical charts. AG anticipates to obtain data from the medical charts of 400-600 patients with advanced RCC. No formal sample size computation was performed as all statistical analyses are descriptive in nature and no hypotheses are being tested.

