8.6. Data Management

This study will collect de-identified data. No patient identifiable information including names or medical record number will be collected in the eCRF. For variables that may contain potentially identifiable information such as number of years in practice, ranges or categories will be used rather than collecting specific values. Furthermore, physicians extracting the data will not retain a decoding key so that the data cannot be linked back to an individual. Lastly, the identity of physicians participating in this study will not be known to AG, Medefield, or Pfizer.

De-identified data collected from the physicians by the physician panel vendor will be transferred to AG over a secured and encrypted network for analysis, and stored in secure servers accessible only by designated personnel working on the project within AG. The minimum retention time will meet the strictest standard applicable for the study, as dictated by the applicable guidelines or applicable laws or regulations.

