8.9. Limitations of the Research Methods

Several limitations should be considered when interpreting findings from this study.

- There is potential for measurement error in data collection, and the use of a standardized, pilot-tested eCRF with data validation checks will address this to some extent. Overall, the quality of data is limited by how well information was recorded in the patients’ medical charts.
- To protect physician and patient anonymity, the collected data cannot be audited against medical records and queries on the accuracy of data entries cannot be conducted. Erroneous data entries can be detected by checking inconsistent responses, but may result in the inability to use certain data points.
- There may be missing information if data have not been recorded in a systematic manner by physicians over time; collecting information on physician characteristics can help understand if missingness is related to physician practice. In addition, AEs never reported to a physician (ie, if they were self-resolved without seeking care), or events not recorded or misclassified in the medical charts, will not be captured. As such, the proportion of management strategies for AEs would only apply to AEs that require healthcare intervention.

- The study is subject to self-reporting bias, including social desirability bias. To minimize the potential for this bias, study materials will emphasize that participation in the survey is anonymous.
- This study is subject to potential selection bias as physicians who elect to participate may differ from those who decline to participate. Demographic and practice characteristics will be presented to describe the sample of physicians enrolled in this study and may be compared to national reports describing similar physician characteristics (eg, Kantar healthcare reports) to provide insight into the generalizability of results.

Despite these limitations, retrospective chart review studies using a panel-based approach are less resource-intensive than prospective cohort studies, allowing for the creation of detailed datasets with information on patient characteristics tailored to specific research questions. Using a physician panel provides direct insight into patient medical history and clinical course, and allows the possibility of supplementing data with physician knowledge when information is not well recorded in patient charts.

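### Physician eligibility rests on chart access, and nothing stops or detects the same patient being abstracted by two oncologists who share records; the likely effect is small and the remedy cheap

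*Combined protocol and SAP*

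**What the plan says.** Section 8.2.1 sets two physician criteria: "Specialty in oncology" and "Access to complete medical records for at least one patient with advanced RCC who meets the patient eligibility criteria". Neither these nor the patient criteria require that the abstractor treated the patient, and section 8.2.2 has no exclusions.

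Section 8.4 adds that "Each oncologist will complete eCRFs for up to three patients". When more than three patients are eligible, the form's program generates random letters and the oncologist takes the first eligible chart under each letter. The draw is specific to that oncologist.

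Section 8.5 states "Approximately 200 oncologists may be recruited by the physician panel vendor to abstract medical charts" and "AG anticipates to obtain data from the medical charts of 400-600 patients with advanced RCC". No section limits the number of participants per practice. The practice-size item in section 8.3.1 has categories running from solo to 51 or more physicians.

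Under section 8.6, names and record numbers are not collected, and "physicians extracting the data will not retain a decoding key so that the data cannot be linked back to an individual". Section 8.9 says that entries can be neither audited against records nor queried. The form checks named in section 8.8 are date validation and range checks; the rest is code review and review of tables. Sections 8.7.1 to 8.7.4 have no de-duplication step, and duplicate patients are not among the limitations in section 8.9.

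Section 8.9 also counts as a strength that the panel approach "allows the possibility of supplementing data with physician knowledge when information is not well recorded in patient charts".

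**The concern.** In a group practice with one record system, several oncologists could meet the access criterion for the same patient. If two of them are on the panel, both can submit that patient. Each table would then count one person as two, and the stated number of patients would be a number of records. Nobody could settle the question afterwards by going back to the chart, so any rule for handling it has to be written beforehand.

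A second, smaller point concerns physician knowledge. Filling gaps in the chart from that knowledge works only if the abstractor knows the patient, and access alone does not secure this. AE resolution and the choice of management strategy are where such knowledge would matter most.

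**Working it through.** **1. The plan's own figure.** 200 oncologists × 3 charts = 600, which reproduces the upper end in section 8.5. The lower end corresponds to 400 / 200 = 2 charts each, an average the plan does not state. Both are counts of records; they equal patients only if nobody is abstracted twice.

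**2. Overlap within one sharing pair.** Assume that two oncologists draw from the same pool of M eligible patients, each taking 3 at random. The documents do not give M; 10, 20 and 30 are assumed.

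- P(at least one shared patient) = 1 − C(M−3, 3) / C(M, 3)
  - M = 10: 1 − 35/120 = 0.708
  - M = 20: 1 − 680/1140 = 0.404
  - M = 30: 1 − 2925/4060 = 0.280
- Expected shared patients = 3 × 3 / M = 9/M = 0.90, 0.45 and 0.30

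The letter rule is not a uniform draw. If both oncologists work from one list in the same order, the expected overlap is the sum of squared selection probabilities. These sum to 3, so the overlap is at least 9/M.

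**3. Study-wide rate.** The share of the 200 oncologists who are in sharing pairs is not given; 10% and 25% are assumed. Expected duplicates = number of pairs × 9/M, over 600 records.

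| Share in pairs | Pairs | M = 10 | M = 20 | M = 30 |
|---|---|---|---|---|
| 10% | 10 | 9 (1.5%) | 4.5 (0.75%) | 3 (0.5%) |
| 25% | 25 | 22.5 (3.75%) | 11.25 (1.9%) | 7.5 (1.25%) |

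**4. Effect on precision.** Take N records of which d are second copies, with both copies giving the same answer, and ignore other clustering. There are N − 2d patients counted once and d counted twice. The variance of a proportion is p(1−p)[(N − 2d) + 4d]/N², an inflation of 1 + 2d/N over the nominal value. With p = 0.5 and half-width 1.96 × √variance:

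- N = 600: nominal 4.00 points. At 0.5% duplicates the inflation is 1.01 and the half-width 4.02; at 3.75% they are 1.075 and 4.15.
- N = 400 with 10% duplicates (d = 40, 360 unique patients): inflation 480/400 = 1.20, so 4.90 points becomes 5.37.
- N = 600 with 10% duplicates (d = 60, 540 unique patients): 4.00 points becomes 4.38.

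**5. Small strata.** Objective 3 splits resolution by management strategy, AE type and seriousness. In a stratum of 20 records (assumed), a single duplicate is 1/20 = 5% of the records.

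**The case against.** The strongest reply is that the authors probably meant each physician's own patients. Section 8.2.1 speaks of an oncologist having more than three eligible patients, section 8.3.1 asks how many such patients the physician sees per year, and section 8.9 counts on physician knowledge. This is a fair reading. It is not, however, what the eligibility criterion says, and if it is the intention, the edit merely writes it down.

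It can also be said that the practice-size categories are questionnaire options. They count physicians rather than oncologists and show nothing about panel members sharing a practice; section 8.4 describes a geographically wide panel. That stands: the plan permits duplication but gives no evidence of how common it would be.

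The study is also descriptive and tests no hypotheses, so a modest loss of precision overturns no conclusion. That stands too, and it limits the weight of the point.

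Four stronger readings are tempting, and the documents do not support them:

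- A reader might take 71%, 40% and 28% as study-wide risks. They apply only to two participants who both draw from one whole shared pool. Likewise, 0.90/6 = 15%, 0.45/6 = 7.5% and 0.30/6 = 5% would be study-wide rates only if all 200 oncologists were so paired.
- A reader might infer that duplication over-weights large groups. Two colleagues contribute six records whether or not a patient overlaps, so that weight comes from how many physicians take part.
- A reader might infer that duplicates can never be found. Confirmation at source is ruled out, but flagging matching records is feasible with the planned data.
- A reader might infer that non-treating abstractors will misclassify AE dates and management. The plan requires complete records and presents physician knowledge only as a possible supplement; it gives nothing from which such an error could be shown or sized.

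**Conclusion.** The point holds as a gap in the stated rules. Eligibility by access, a separate draw for each oncologist and the absence of a cross-record check together allow one patient to enter twice, with no way of confirming it later. It is a cheap improvement worth making, not a threat to the study.

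The size is uncertain because the documents give neither the frequency of shared practices nor the pool sizes. Under the assumed ranges, about 0.5-4% of 600 records would be duplicates, and the overall 95% half-width would rise from 4.00 to at most about 4.15 points. Even an assumed 10% at N = 400 adds only 5.37 − 4.90 = 0.47 points. The calculation treats draws as uniform, and the letter rule could raise the overlap. The effect could be larger in small strata.

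**What to change.** In section 8.2.1, require that the oncologist treated the patient, or shares primary responsibility for the patient's first-line axitinib/IO therapy, and has access to the complete record. This also secures the knowledge of the patient that section 8.9 counts as a strength. Shared care could still produce duplicates, so the criterion is not enough by itself.

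Add a pre-analysis step to sections 8.7 and 8.8:

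- Flag records from different oncologists that match or nearly match on birth month and year, sex, region, advanced RCC diagnosis date, combination start date and IO agent. All are already collected under sections 8.3.1 and 8.3.2. Near matches are needed because two abstractors may record a date differently.
- For exact matches, keep one record by a rule set in advance, for example the more complete record, then the first submitted.
- Report the number of records flagged, and run a sensitivity analysis excluding near matches.

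The cost is one screener question and one data-cleaning step, with no new patient identifiers. Section 8.4.1 already foresees form and protocol updates after the pilot. The downside is slightly fewer eligible charts for some oncologists and the rare loss of a coincidental match.
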